# 9.2.8. Patients on greater than 4mg per day of dexamethasone within the 2 weeks prior to admission for PVSRIPO infusion

[figure not shown]
- 9.2.9. Patients with worsening steroid myopathy (history of gradual progression of bilateral proximal muscle weakness, and atrophy of proximal muscle groups)
- 9.2.10. Patients with prior, unrelated malignancy requiring current active treatment with the exception of cervical carcinoma in situ and adequately treated basal cell or squamous cell carcinoma of the skin

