Furthermore, patients previously treated on trial received high dose steroids prior to catheter insertion and throughout the infusion, as part of undergoing biopsy. Given concerns for negative impact of high dose steroids on the efficacy of PVSRIPO, we will limit steroid usage to the minimal dose necessary, if even needed.

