#### **11.4.1. Definition of Dose-limiting Toxicity**

Dose-limiting toxicity (DLT) will be defined using the NCI Common Toxicity Criteria (CTC) (Version 4). Any Grade 3 or any Grade 4 toxicity that is not reversible within 2 weeks, or any life-threatening event, or treatment-related death will be considered a DLT. Any grade 2 or higher serious autoimmune toxicities particularly those affecting vital organs (e.g. cardiac, renal, CNS) will be considered a DLT if it occurs within 2 weeks with or without treatment. Exceptions to these DLT's are as follows:

- Events associated with the biopsy procedure/catheter placement: seizures or hemorrhages occurring during anesthesia or the biopsy/catheter insertion proper prior to administration of the agent if Grade 2 or lower (Grade 3 or higher surgical complication from insertion of catheter is considered DLT).
- Seizures: Due to the nature of the disease under investigation in this protocol, patients may have pre-existing seizures or be susceptible to new seizures as a result of the underlying disease process. Although seizures may be defined as Grade 3 or 4 toxicities under NCI CTC, and will be reported as such in this protocol, seizures will not be considered DLT if, in the opinion of the Principal Investigator they have not increased in frequency or can be attributed to another recognized cause of increasing seizure frequency such as sub-therapeutic anti-convulsant levels or biopsy proven tumor progression.
- New neurologic deficits: Due to the nature of the disease under investigation in this protocol, patients may develop new neurologic deficits as a result of tumor invasion. A new neurologic deficit, which resolves within 2 weeks after initiation of medical therapy, will not be considered a DLT. Similarly, late (≥ 4 weeks after completion of infusion) DLTs thought to be drug or procedure related, which resolves within 2 weeks after initiation of medical therapy, will not be considered a DLT. New neurological symptoms will not be a DLT if they can be ascribed to tumor

progression (e.g. documented with histopathologic analyses of biopsy tissue; or; they respond to treatment (e.g. oral steroids, within 2 weeks)).

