- Thromboembolism: Due to the high incidence of deep vein thrombosis (DVT) in this patient population, patients may have undiagnosed pre-existing DVTs or be susceptible to the development of DVTs due to the underlying disease process. Although DVT may be defined as Grade 3 or 4 toxicities under NCI CTC, and will be reported as such in this protocol, DVT will not be considered DLT in this protocol.
- Syndrome of Inappropriate Antidiuretic Hormone (SIADH): Due to the high incidence of SIADH in this patient population, patients may be susceptible to the development of SIADH due to the underlying disease process. Although SIADH may be defined as Grade 3 toxicity under NCI CTC, and will be reported as such in this protocol, SIADH will not be considered DLT in this protocol unless it is refractory to medical management.
- Muscle Weakness and Weight Gain: Due to the high incidence of muscle weakness and weight gain in patients taking steroids in this patient population, patients may be susceptible to the development of muscle weakness or weight gain which is due to steroids alone. Although muscle weakness may be defined as Grade 3 or Grade 4 toxicity and weight gain ≥ 20% may be defined as Grade 3 toxicity under NCI CTC, and will be reported as such in this protocol, muscle weakness or weight gain will not be considered DLT in this protocol if the patient has required steroids greater than physiologic doses in the interval between the immunization and the development of the toxicity.
- Tumor Progression: Due to the nature of the disease under investigation in this protocol, patients may have an increase in pre-existing neurologic deficits or have an onset of new neurologic deficits due to tumor progression. Although such neurologic deficits may be defined as DLTs under NCI CTC, and will be reported as such in this protocol, these clinical changes are not an unexpected phenomenon in this disease in the setting of tumor growth. As a result, neurologic deficits will not be considered a DLT if unequivocal tumor progression can be documented radiographically or histologically.

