#### 15.2.3. Poliomyelitis

PVSRIPO has been tested in NHPs according to the WHO standardized monkey neurovirulence tests. These tests revealed the absence of neuropathogenic properties, evident as failure to induce symptoms of poliomyelitis in NHPs after intracerebral inoculation of virus. However, PVSRIPO are replication-competent viral agents that, in principle, retain the potential to cause motor neuron damage. Possible complications include transient or permanent mono- or paraparesis, paralysis, and life-threatening respiratory insufficiency.

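### The muscle-weakness exemption in 11.4.1 tests steroid exposure, not cause, so a PVSRIPO-related paresis recorded as muscle weakness could be left out of the DLT count

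*Combined protocol and SAP*

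**What the plan says.** Section 11.4.1 gives a general rule: "Any Grade 3 or any Grade 4 toxicity that is not reversible within 2 weeks, or any life-threatening event, or treatment-related death" is a DLT. A list of exceptions follows.

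- **Muscle weakness and weight gain.** The reason given is that "patients may be susceptible to the development of muscle weakness or weight gain which is due to steroids alone". The operative clause is that "muscle weakness or weight gain will not be considered DLT in this protocol if the patient has required steroids greater than physiologic doses". Steroid use counts at any time from the immunization, a term left undefined, to the onset of the event. The clause covers weakness of Grade 3 or Grade 4, which is still to be reported as such.
- **New neurologic deficits.** A deficit is exempt if it resolves within two weeks of starting medical therapy, or if it can be ascribed to tumor progression. Steroid use is not a condition for this exemption.

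Section 15.2.3 warns that the virus could in principle damage motor neurons: "Possible complications include transient or permanent mono- or paraparesis, paralysis, and life-threatening respiratory insufficiency". On steroid exposure, section 11.3.8 (AMD096) records that "patients previously treated on trial received high dose steroids prior to catheter insertion and throughout the infusion", and says that use will be kept to a minimum from then on.

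Section 11.4 states that dose level 2 was declared the MTD because no DLT occurred there, and that DLT monitoring ended on 10/06/2014. Section 11.5 then carries a DLT definition forward as the definition of unacceptable toxicity, with a 25% suspension threshold for dose levels -1 and -2. It cites 11.4.2 for that definition. Section 11.6 applies the same guidelines to retreatment.

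**The concern.** The rule does not match its rationale. The rationale concerns weakness that steroids alone explain; the rule asks only whether the patient needed steroids above physiologic doses at some time in an interval. It does not ask what caused the weakness, and neither the start of the interval nor the dose threshold is defined.

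This matters more for weakness than for most exempted events, because motor weakness is one of the agent's own listed risks. If a persistent paresis can be filed under either of two items with different conditions, the choice of adverse event term can decide whether it is a DLT. DLT is the measure behind the MTD. If the exemption also carries into 11.5 and 11.6, it affects the suspension rule for the expansion cohorts and for retreatment.

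**Working it through.** The plan gives no figure for this clause, so there is none to reproduce. The check has four parts.

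**1. Rule against rationale.** Other items in the same list carry limits. Seizures need the investigator's judgement on frequency or another recognized cause. SIADH counts if refractory to medical management. Progression must be unequivocal on imaging or histology. The weakness item has only the steroid condition. The one looser item is deep vein thrombosis, which section 15.2 does not list as a risk of the agent.

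**2. Which item governs.** Take a Grade 3 limb paresis that lasts beyond two weeks, is not ascribed to progression, and occurs in a patient who had high-dose steroids around the biopsy.

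- Recorded as a new neurologic deficit, it meets no exception and is a DLT.
- Recorded as muscle weakness, it meets the steroid condition and is not a DLT.

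Both items are exceptions, and no precedence is stated. Failing one does not clearly restore DLT status if the other applies.

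**3. How many patients met the steroid condition.** Assumptions: the immunization is the polio booster, given at least 1 week before infusion (9.1.5) and up to 6 months before it (Table 5), so that peri-procedural steroids fall inside the interval; routine high-dose peri-procedural steroids count as having required them; and the current wording applied throughout.

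- Treated by 6/15/2015: 28, of whom 13 at level -1 (14.3.1). Other levels: 28 - 13 = 15.
- Treated at level -1 by 6/15/2016, before AMD096 took effect: 23 (11.3.8).
- Total before AMD096: 15 + 23 = 38.
- Share of the 51 treated by 1/20/2017 (11.3.11): 38/51 = 75%.
- Share of the 59 subjects in the shedding report (11.3.13): 38/59 = 64%.
- Within levels -1 and -2, the population of 11.5: 23/(51 - 15) = 23/36 = 64%, or 23/(59 - 15) = 23/44 = 52%.

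With 14 rather than 15 patients at the other levels, the shares are 37/51 = 73%, 37/59 = 63%, 23/37 = 62% and 23/45 = 51%.

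**4. What it could do to the 25% rule.** This is an illustration and an upper limit. It supposes that the exemption carries over to 11.5, that every unacceptable event is weakness, and that a share q of those events is exempt. For a true event rate p, the chance of meeting the trigger is P(X ≥ 0.25n), where X is binomial with parameters n and p(1 - q). The documents give neither p nor q. The 64% and 52% are the exposure shares from step 3.

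| n (trigger) | q | p = 25% | p = 35% | p = 50% |
|---|---|---|---|---|
| 36 (9) | 0 | 56% | 93% | 99.9% |
| 36 (9) | 25% | 22% | 63% | 96% |
| 36 (9) | 64% | 0.4% | 3% | 19% |
| 44 (11) | 0 | 56% | 94% | 100% (rounded) |
| 44 (11) | 25% | 19% | 63% | 97% |
| 44 (11) | 52% | 1% | 11% | 50% |

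Weakness would be only part of the real event mix, so the true effect would be smaller.

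**The case against.** A reader might infer that virus-induced paresis would not count as a DLT or unacceptable toxicity in most patients, so that the safety endpoint cannot detect it. The documents do not support that, for five reasons.

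- Paresis and paralysis fit the new-neurologic-deficit item at least as naturally. Respiratory insufficiency, also named in 15.2.3, is not muscle weakness.
- Read as literally as 11.4.1, section 11.5 points to 11.4.2, which does not contain the exemption. Carry-over requires reading the citation as 11.4.1. That is plausible, since 11.4.1 is the section titled as the definition and 11.4.2 concerns management, but it is an inference.
- The 38 rest on practice before AMD096. Steroids were minimized afterwards, and 11.3.8 says that level -1 patients stayed off significant doses.
- Exempted weakness is still graded and reported. Section 11.5 allows suspension for other safety concerns and requires six-monthly review. Persistent disability is a serious adverse event under 16.5, and 16.6 adds roughly weekly event review and a DSMB-Plus.
- DLT monitoring ended in 2014, new enrollment closed in June 2017 (16.6), and the return to level -1 rested on comparable bevacizumab need and similar toxicity profiles (11.3.11), not on DLT counts.

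All five points stand, and they limit the finding. They do not remove it. The deficit item is itself an exception and has no stated priority, and the reviews do not correct a count from which an event has been dropped. The no-DLT statement for level 2 is one such count: six of eight subjects treated at that level had trouble tapering steroids beyond three months (11.3.3).

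**Conclusion.** The concern holds in limited form. The exemption is broader than its own rationale, and a persistent Grade 3-4 PVSRIPO-related paresis recorded as muscle weakness could be left out of the DLT count. On a literal reading and the assumptions in step 3, about 38 patients met the exposure condition: 75% or 64% of all treated, and 64% or 52% within levels -1 and -2. A majority is not established for patients treated after AMD096. Whether the 25% rule in 11.5 and 11.6 is affected cannot be settled from the text.

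This is a defect in how an event is classified, not evidence of harm: the documents report no exempted paresis. What remains at stake is retreatment monitoring and the final safety report. A statement that no DLT occurred should not, by itself, be read as saying that no persistent Grade 3-4 weakness occurred.

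**What to change.** 1. Reconcile 11.4.1 with its stated rationale and with 15.2.3, so that the exemption applies only to weakness attributed to steroids alone. The clinical criteria for that attribution are for the investigators to set. Section 9.2.9 already describes steroid myopathy ("history of gradual progression of bilateral proximal muscle weakness, and atrophy of proximal muscle groups"), but as an eligibility exclusion, not as an attribution rule.
2. State whether the weakness item or the new-neurologic-deficit item governs weakness of possible motor-neuron origin.
3. Define the immunization and physiologic doses. Moving the start of the interval to the infusion would not be enough, because before AMD096 steroids ran throughout the infusion.
4. Correct or confirm the citation of 11.4.2 in 11.5, which 11.6 relies on.
5. Re-classify recorded Grade 3-4 weakness events under the reconciled wording before reporting, and give DLT and unacceptable-toxicity counts both with and without exempted weakness.

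The cost is a short amendment and a re-review of existing Grade 3-4 weakness records. Neurologic examinations are already done at each follow-up visit (12.2), so no new data are needed. The small downside is that a few more events may count.

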#### 11.4.2. Management of Toxicities

If a Grade 3 or 4 NCI CTC toxicity is observed, the patient will be monitored until the NCI CTC toxicity improves to a Grade 1. If this resolves within 4 weeks with or without treatment, these toxicities will not be considered dose limiting. If a new Grade 3 or 4 NCI CTC toxicity is seen again in the same subject after initial resolution within 4 weeks of the initial infusion, a DLT will be declared.

If Grade 2 or higher serious autoimmune NCI CTC toxicity is observed the patient will be monitored until the NCI CTC toxicity improves to a Grade 1. If resolution to Grade 1 occurs within 4 weeks with or without treatment, these toxicities will not be considered dose limiting.

#### 11.5. TOXICITY MONITORING AFTER DOSE ESCALATION

Though DLT monitoring has been discontinued due to the declaration of dose level 2 as the MTD, toxicity monitoring continues. Specifically, the study is being monitored for the occurrence of unacceptable toxicities within dose levels -1 and -2 at any time after the initiation of protocol treatment. We will use the definition of DLT provided in section 11.4.2 as the definition of an unacceptable toxicity.

Given that both long- and short-term toxicities are of interest, it is not feasible to suspend accrual while toxicity is assessed as was done within the dose-escalation portion of this study. If 25% or more of patients have experienced an unacceptable adverse event or there are other reasons for concern about the safety of patient treatment (e.g. treatment-related toxic death), accrual will be suspended and data will be carefully reviewed to determine if accrual should be permanently terminated or the protocol modified. These guidelines have not been adjusted for differential length of follow-up of accrued patients.

Every 6 months, the toxicity experienced by patients accrued to this study will be summarized and reviewed, regardless of the number of patients accrued, to determine whether the overall toxicity profile of treatment is unacceptable or not.

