### **11.4. DOSE-LIMITING TOXICITY**

Patients will be monitored for toxicity indefinitely or until confirmation of recurrent disease or the patient prematurely discontinues from the study at Duke University Medical Center. Adverse events will be categorized and graded in accordance with the NCI CTC (Version 4).

During the dose escalation phase of this study, patients were also monitored for dose-limiting toxicity (DLT). As no patient experienced a DLT on dose level 2, dose level 2 was determined to be the MTD. On 10/06/2014, the protocol was amended to reduce the dose to dose level -1 (see section 11.3.3). Since dose level 2 was determined to be the MTD, DLT monitoring was discontinued at that time.

With the removal of oversight by the study-specific DSMB, a patient summary with toxicity review will no longer need to be generated after each patient (see section 11.3.9).

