### 11.6. TOXICITY MONITORING OF PVSRIPO RETREATMENT

Though there is growing knowledge about the long- and short-term toxicities associated with an initial PVSRIPO infusion, there is a possibility that the toxicities associated with a second infusion might differ in some manner from the initial infusion. Hence, the toxicity monitoring that has occurred with the initial PVSRIPO infusion will continue with the second PVSRIPO infusion. The guidelines provided in section 11.5 will also be implemented in the monitoring of toxicity associated with the second infusion of PVSRIPO.

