### 11.7. DISCHARGE, FOLLOW-UP AND DURATION OF STUDY

Patients will be followed at a minimum of 2, 4, 8, 16, 24, 32, 40 and 48 week intervals after infusion as outlined in the Study Test Schema (see section 18.1).

Patients may not be treated with any other modality (other than bevacizumab per the 'special considerations' in section 15.2.7) unless progressive tumor is noted or they are otherwise removed from the study. Patients will be considered off study upon tumor progression or upon treatment of the tumor with another modality. When subjects are considered off study, this indicates that subjects will no longer be obligated to undergo study-related tests and procedures, but the data described below will still be collected from these subjects as feasible. Subjects will be followed for serious adverse events for 30 days after coming off study. Collection of the following additional data from off study subjects will be performed, if possible, but is not mandatory and will not be considered a deviation if the data cannot be obtained. Subject's medical records will be reviewed for the remainder of their life, in order to follow survival, as will subjects' MRIs. Subjects will also be followed for progression and subsequent treatments. Follow-up activity will be at the discretion of the treating physician.

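### The 25% toxicity guideline has an any-time target, but adverse-event collection ends at or soon after off study, so the counted rate can equal or understate that target by an unknown amount

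*Combined protocol and SAP*

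**What the plan says.** Section 11.5 replaces the dose-escalation DLT rule with monitoring of "unacceptable toxicities within dose levels -1 and -2 at any time after the initiation of protocol treatment". It gives as a reason: "Given that both long- and short-term toxicities are of interest". Accrual is suspended and the data reviewed on this condition: "If 25% or more of patients have experienced an unacceptable adverse event". Other safety concerns, such as a treatment-related toxic death, can also trigger suspension. The section adds: "These guidelines have not been adjusted for differential length of follow-up of accrued patients". Toxicity is also summarised every 6 months.

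Two other sections say how long toxicity is collected. Section 11.4: "Patients will be monitored for toxicity indefinitely or until confirmation of recurrent disease or the patient prematurely discontinues from the study". Section 11.7 takes a patient off study at tumour progression or when the tumour is treated with another modality, other than bevacizumab under 15.2.7. It then says: "Subjects will be followed for serious adverse events for 30 days after coming off study". The further off-study data in 11.7 are collected where possible but are not mandatory. They are survival, MRIs, progression and subsequent treatments; adverse events are not among them.

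Section 11.6 carries the rule to retreatment: "The guidelines provided in section 11.5 will also be implemented in the monitoring of toxicity associated with the second infusion of PVSRIPO".

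**The concern.** The target in 11.5 has no end date, but the data that feed it do. An unacceptable toxicity need not be a serious adverse event. Under 11.4.1 it can be a Grade 3 toxicity that does not reverse within 2 weeks, and such an event need not meet the seriousness criteria in 16.5. A non-serious qualifying event can therefore go unrecorded from the day the patient leaves the study, and a serious one from day 31.

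Nothing in 11.5 removes these patients from the denominator or weights them by follow-up. A patient whose collection has ended without an event then counts the same as one observed event-free for the whole period. At stake are the 25% guideline, the 6-monthly summaries, the toxicity rates reported for dose levels -1 and -2, and retreatment monitoring under 11.6.

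**Working it through.** The documents state no trigger probability for the 25% guideline, so there is no plan figure to reproduce. The direction follows from the text. The size needs assumptions.

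**Direction.** Let p be the true any-time rate and q the share of qualifying patients whose event falls after collection ends. With all treated patients in the denominator, the counted rate is p × (1 − q), which is at most p. It equals p only if q = 0.

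**Inputs.**
- n = 44 at dose levels -1 and -2. This is 59 treated subjects (11.3.13) minus the 15 not at dose level -1 in June 2015 (28 − 13, section 14.3.1). It assumes that all 59 were treated on this protocol and that the two levels are pooled. The threshold is 0.25 × 44 = 11 patients.
- True 12-month rate 30% (assumed).
- Time to off study exponential with a 4-month median, varied from 3 to 9 months (assumed). Death is ignored.

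**Full collection.** P(X ≥ 11), with X binomial(44, 0.30), is 81%.

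**Constant hazard, collection ending at off study.**
- λ = −ln(0.70)/12 = 0.0297 per month; μ = ln 2/4 = 0.1733 per month.
- Counted rate = λ/(λ+μ) × (1 − exp(−12(λ+μ))) = 0.1464 × 0.9125 = 13.4%.
- P(X ≥ 11) is about 3%.
- For medians of 3, 6 and 9 months the counted rate is 11%, 17% and 20%, and the chance is about 1%, 11% and 26%.
- If every event in the month after off study is also captured, the 4-month counted rate is (1 − exp(−λ)) + exp(−λ) × 0.1464 × (1 − exp(−11(λ+μ))) = 0.0293 + 0.1269 = 15.6%, and the chance is about 7%.

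**Front-loaded events, 4-month median.** Assume 80% of events spread evenly over month 1 and 20% over months 2 to 12.
- Collection ending at off study: share captured is (1 − exp(−μ))/μ = 0.918 in month 1 and (exp(−μ) − exp(−12μ))/(11μ) = 0.376 later. Overall 0.8 × 0.918 + 0.2 × 0.376 = 0.810. Counted rate 0.30 × 0.810 = 24.3%; chance about 51%.
- Every event in the following month also captured: 1.000 and (1 − exp(−11μ))/(11μ) = 0.447. Overall 0.889. Counted rate 26.7%; chance about 66%. This is an upper bound, because only serious events are followed in that month.

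**All qualifying events before off study.** q = 0, and the chance stays at 81%.

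**Second check, with death included.** A simulation used exponential survival with the 15.2-month median in 14.3.1, assumed median PFS from 9 down to 2 months, and collection to progression plus 1 month or death. The missed share q was 7% to 16% if 80% of toxicities are early, 16% to 40% if half are early, and 27% to 77% if risk is constant until death. For the planned 50 patients at dose level -1 (threshold 13) and a true rate of 30%, the chance of reaching the threshold is 0.78, 0.62, 0.33 and 0.03 for q of 0, 10%, 25% and 50%.

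**The case against.** The strongest reply is that the wording differs but the consequence may be small. Five parts of it deserve an answer.

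- The any-time wording in 11.5 may only contrast with the 4-week DLT window in 11.1.5.1, and so mean no fixed cut-off within the monitored period of 11.4. On that reading the cut-off causes no bias. The reading is possible, but 11.5 does not state it. The all-treated denominator is likewise the natural reading, not a written one.
- The lack of adjustment for follow-up is disclosed. A reader might take that caveat to cover only recently accrued patients, but the text has no such limit. What stands is that no follow-up-adjusted estimate is planned and that the caveat does not mention collection ending by rule.
- A reader might infer that patients with burdensome inflammation are the ones who leave toxicity collection. The documents do not support this. Bevacizumab for inflammation under 15.2.7 is exempt in 11.7 and 11.8, and those patients continue on a 9-week schedule. The loss applies to patients judged progressed or given another modality such as chemotherapy. Section 11.3.8 reports 9 of 12 patients needing prolonged bevacizumab and/or additional chemotherapy, without saying how many had chemotherapy. Section 13.1 does say that inflammation and progression are hard to tell apart, so some informative loss is possible, but its extent is unknown.
- Many late events would not qualify. Section 11.4.1 exempts neurologic deficits with unequivocal progression, DVT, SIADH that is not refractory, and some late events that resolve. Events after another therapy are hard to attribute. This limits the size but does not remove the gap.
- Other safeguards exist: suspension for other safety concerns, 6-monthly reviews, weekly adverse-event meetings, the DSMB-Plus, and adverse events listed as continuous in Table 6. None of them states a collection window after off study. Section 16.6 records closure of new enrolment in June 2017, so a pause calculated on 44 patients now has little operational effect.

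**Conclusion.** The mismatch between the target in 11.5 and the collection rules in 11.4 and 11.7 is real. If the target is any-time toxicity and the denominator is all treated patients, the counted rate can only equal or understate it. The size cannot be derived from the documents. In the 44-patient scenario with a true rate of 30% and a 4-month median, the chance of reaching 25% runs from about 3% (constant hazard), through 51% to 66% (80% of events in month 1), to an unchanged 81% (all events before off study). These are scenarios, not estimates.

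A reader might conclude that the toxicity rates for dose levels -1 and -2 are known to be biased low, or that the guideline almost never triggers. The documents support neither. The first needs qualifying events after collection ends, which may not occur. The second rests on the constant-hazard case, which is doubtful after a single infusion with surgical and acute inflammatory risks. With new enrolment closed, the practical effect is on the reported toxicity rates and on retreatment monitoring. Correction is worth making but is not critical.

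**What to change.** Reconcile the windows in 11.4, 11.5 and 11.7 by one of two routes:

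1. Keep the any-time target. Make it a listed off-study item to abstract, from the medical records that 11.7 already reviews for life, any event meeting the unacceptable-toxicity definition and any serious event possibly related to PVSRIPO.
2. Restate the 11.5 target as toxicity up to the end of collection.

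Under either route, define the denominator, including whether the two dose levels are pooled. In each 6-monthly review and the final toxicity report, show beside the crude percentage the number of patients still under full collection and the cumulative incidence, censored at the end of collection with death as a competing event. Do the same from the second infusion under 11.6. That censoring assumes that leaving collection is unrelated to later toxicity. Section 13.1 gives reason to doubt this, which favours the first route.

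Section 11.5 also takes its definition from 11.4.2, whereas the definition stands in 11.4.1, and the two give different resolution periods (4 weeks and 2 weeks). Those passages must be reconciled before events are abstracted.

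The cost is amended wording in three sections, one extra item from records already under review, and one added table. The downsides are a slightly higher reported rate and the need to attribute late events after other therapy.
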